## 6.2 FIDELITY

### 6.2.1 INTERVENTIONIST TRAINING AND TRACKING

The mentors are the interventionists in this study. Initial training will be evaluated and confirmed using knowledge surveys, and evaluations by the trainer of skills during training. During the intervention program monthly and quarterly surveys by the study team will be used to identify problems with delivering the intervention as planned. As described above, phone records will also be used to evaluate frequency and dosing of attempts and successful calls. These records will be reviewed as frequently as monthly, but not less than every four months. Less than 10 minutes total of contact time between mentor and mentee in one month will prompt addressing barriers to executing the intervention for both mentor and mentee by the study team.

## 6.3 MEASURES TO MINIMIZE BIAS: RANDOMIZATION AND BLINDING

We will randomize enrolled patient participants after completion of informed consent and the baseline visit utilizing a random number generator. As each subject is enrolled we will select envelopes with the random assignment to either the intervention or the usual care control group (1:1). The randomization will occur in blocks of between 28 to 42 depending upon the number of mentor and planned assigned mentees at the site. The goal is to have approximately equal total number of enrolled participants within each ~3-month intervention period. There may be staggering of the window and timeline depending upon enrollment pacing.

The mentee assignments will be blinded to usual care nephrologist and dialysis staff, but not to study subjects and mentors, because of the nature of intervention. The research team additionally will not be blinded to group assignment. While this may be preferred, it is not feasible in this pragmatic trial.

Enrolled participants will be encouraged to complete visit surveys on their own, to limit interactions with study staff in the process of data collection.

Trial randomization codes will be stored in a single file maintained by the data coordinating center. They will be shared with the research team as described above for patient participant assignment. Should accidental unblinding occur prior to completion of a baseline visit for a participant, the PI will be notified and this will be documented as a protocol deviation.

No change in study activities will occur in the event that it is identified that a usual care provider is unblinded to study assignment of their patient.

#### 6.4 STUDY INTERVENTION/EXPERIMENTAL MANIPULATION ADHERENCE

Adherence of mentees to the peer support intervention will be monitored by the research team including monthly surveys with the mentee asking about the calls with their mentors, as well as review of phone records (See Section 6.2.1). For mentees not participating in calls with mentor the study team will attempt to identify and address the barriers to participation. If pairs want to disengage, we will give the option of pairing with another mentor/mentee from the pool.

Attendance records and notes for participation in any social mixers (in-person or video) will also be maintained and reviewed for assessment of mentee participation in the intervention, including engagement with mentors.

Although all activities are intended and preferred, mentees will not be withdrawn for not participating in the intervention. They will be included in the primary study analysis as intention-to-treat. Secondary analyses may include an adjustment variable considering the dose delivered of the intervention.

#### 6.5 CONCOMITANT THERAPY

N/A

##### 6.5.1 RESCUE THERAPY

N/A

### 7 STUDY INTERVENTION/EXPERIMENTAL MANIPULATION DISCONTINUATION AND PARTICIPANT DISCONTINUATION/WITHDRAWAL

#### 7.1 DISCONTINUATION OF STUDY INTERVENTION/EXPERIMENTAL MANIPULATION

Conflicts or emotional distress may rise between mentors and paired mentees. The study team will get information from both mentor and mentee and determine the nature and severity of the conflict. If there are any concerns regarding emotional or physical safety of participants this will be recorded as an adverse event, reported to the DSMB and the participant(s) withdrawn from the intervention. The participant(s) may also be considered for withdrawal from the study overall depending upon the nature and severity of the event(s).

A mentor may decide to discontinue the study in case of clinical illness, inability to commit to the intervention schedule, or for any other personal reason. Participants may withdraw from the intervention at any time by notifying the study personnel. Mentors may be withdrawn from the intervention due to acute or temporary illness, but may be reconsidered for reactivation if agreed upon by the mentor and the study investigator. Mentors may be discontinued from the intervention if the study team is unable to reach them or they do not fulfil their mentor responsibilities. Mentors who receive a kidney transplant may continue as mentors, but EMR data specific to dialysis will not be collected by the study. Other study visit activities including surveys will be collected.

A mentee may decide to discontinue the study in case of severe illness, conflict, or inability to participate. The PIs at each site will maintain a record of these events and drop-outs and report them to the DSMB or IRB as required.

The PIs at each site will maintain a record of all adverse events, unanticipated problems, protocol

deviations or error. A summary of these will be reported to the IRB. These events will all be reviewed as potential reasons for discontinuation of the intervention (mentor or mentee), or withdrawal from the study overall. The PIs will be primarily responsible for this decision, however this will be reviewed by the DSMB, and if recommended an experienced clinician external to the study team.

If a clinically significant finding is identified (including, but not limited to changes from baseline) after enrollment, the investigator or qualified designee will determine if any change in participant management is needed. Any new clinically relevant finding will be reported as an adverse event (AE).

The data to be collected at the time of study intervention discontinuation will include the following:

- The reason(s) for discontinuing the participant from the intervention and the date the intervention ceased will be recorded in the subject's research file
- Study assessments including visits for survey completion and EMR review will continue as per the usual assigned scheduled throughout the duration of the overall study period

## 7.2 PARTICIPANT DISCONTINUATION/WITHDRAWAL FROM THE STUDY

Participants are free to withdraw from participation in the study at any time upon request.

An investigator may discontinue a participant from the study for the following reasons:

- Lost-to-follow up; unable to contact subject (see **Section 7.3, Lost to Follow-Up**)
- Any event or medical condition or situation occurs such that continued collection of follow-up study data would not be in the best interest of the participant or might require an additional treatment that would confound the interpretation of the study
  - Death
  - illness requiring institutionalization or a change in their dialysis unit
  - illness of a mentor that leaves them unable to fulfil their mentor role in any way
- The participant meets an exclusion criterion (either newly developed or not previously recognized) that precludes further study participation such as:
  - Receipt of a kidney transplant (patient participant mentee or usual care)
  - Change in mentation or cognition rendering the participant unable to participate, including suicidality
  - A change in the willingness of the participant to continue
  - A safety altercation between the paired participants
  - Verbal abuse or threats of physical abuse of any kind
- If the participant is to be discontinued but is medically able and willing, the T2 surveys will be administered at the time of discontinuation. Monthly EMR review will also end at the time of the T2 survey completion or date of discontinuation as determined by the PI.

The reason for discontinuation or withdrawal will be recorded on the withdrawal study form. Subjects who sign the informed consent form and are randomized, but do not receive the study intervention may be replaced. Subjects who sign the informed consent form, and are randomized and receive the study intervention, and subsequently withdraw, or are discontinued from the study, will not be replaced.

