## 9.3 POPULATIONS FOR ANALYSES

For the primary endpoint comparison, an intention-to-treat analysis will be used, including all available data on randomized participants. It is expected that up to 20% of randomized participants may discontinue from the study prior to the end point. These participants will be included in the primary analysis and data from the monthly outcome ascertainment up until the last available time point will be used. As preparation for the follow-up period modification, events to date were evaluated at one site (Einstein) and were found to be more frequent than initial estimates. This informed the request for reduction in the follow-up period.

The characteristics of those who do not complete all study activities will be compared to those with complete follow-up to examine for potential biases introduced by differential follow-up among the two groups. These will be considered ancillary analyses.

Secondary analyses will examine additionally an as-treated population. This will group any intervention patient who did not participate in more than 20 minutes total of the intervention during the three-month period to be classified as the usual care group.

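### Section 7.2 ends record review for the primary endpoint at study discontinuation, so follow-up is needlessly incomplete and the rate ratio can be biased if the arms differ in discontinuation or in later event rates

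*Combined protocol and SAP*

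**What the plan says.** Section 7.2 sets the stopping rule for participants discontinued from the study: "Monthly EMR review will also end at the time of the T2 survey completion or date of discontinuation as determined by the PI". Those who are able and willing complete the T2 surveys at that moment, so both routes in the sentence end outcome collection early. The listed reasons include "Lost-to-follow up; unable to contact subject", "illness requiring institutionalization or a change in their dialysis unit" and "A safety altercation between the paired participants", as well as death, transplant, change in cognition and unwillingness to continue.

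Section 7.1 treats participants who stop only the intervention differently. For them, "EMR review will continue as per the usual assigned scheduled". On withdrawal from the intervention or the study, 7.1 states: "The PIs will be primarily responsible for this decision, however this will be reviewed by the DSMB". Section 6.3 adds: "The research team additionally will not be blinded to group assignment".

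For the primary endpoint, Section 9.3 states that "an intention-to-treat analysis will be used, including all available data on randomized participants". It expects up to 20% to discontinue and uses their monthly data to the last available time point. Section 9.4.2 finds events each month from both self-report and medical records, and fits a Poisson mixed model with log follow-up time as offset. Section 8.1 says the records come from clinical care, under a HIPAA authorization given with consent.

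**The concern.** A participant who cannot be reached, is institutionalized, has a change in cognition or has fallen out with a mentor is still at risk of ED visits and admissions. Those events will often still be visible in the clinical record. Section 4.4 already has the team read the EHR for 30 days after T2 for serious adverse events, so reading records after the last visit is not foreign to this trial. Section 7.2 nonetheless stops the review.

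Two things are at stake. The first is precision, because person-time that could have been collected is lost. The second is bias. The offset adjusts for shorter observation, but it assumes that the rate seen before the cut-off also describes the time after it. If sicker participants leave, that assumption fails. If leaving also differs by arm, the error does not cancel in the rate ratio. Arm-dependent leaving is plausible here: among randomized participants, a conflict with a mentor can arise only in the intervention arm. For the reasons without a natural date, the person who fixes the cut-off knows the assignment.

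**Working it through.** **Inputs from the documents.** Control rate 0.27 per person-month, 20% reduction (to 0.216), 73 per group after 25% drop-out, at least 100 recruited per group, type 1 error 0.05 (Section 9.2); two-sided tests (9.4.1); up to 20% discontinuing (9.3); 18 months' observation originally, 12 months for new participants (1.1, 1.2).

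**Plan's own figure.** Power = Φ(|ln 0.8| / √(1/E0 + 1/E1) − 1.96), where E is expected events per arm. Section 9.2 gives no follow-up time; 18 months is assumed.
- E0 = 73 × 18 × 0.27 = 354.8 and E1 = 73 × 18 × 0.216 = 283.8.
- Power = 80.0%, so the stated figure reproduces.

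**Precision at 12 months, 100 per arm.**
- Records followed to month 12 for all: 1,200 person-months per arm, E0 = 324.0, E1 = 259.2, power 76%.
- Review stopped in 20%, on average halfway: 1,200 × (0.80 + 0.20 × 0.5) = 1,080 person-months, a 10% loss, power 72%.
- Range over 15-25% discontinuing at 25-75% of follow-up: 3.75-18.75% of person-months lost, power 74.8% down to 67.5%.

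These figures assume no overdispersion or clustering, either of which would lower them. The higher event frequency reported from one site in Section 9.3 would raise them.

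**Bias.** Assume that discontinuers have the same rate r as others until they stop at mid-follow-up, and k times that rate afterwards. With a fraction d discontinuing, the truncated arm rate is r and the full-follow-up rate is r × [1 + d(k − 1)/2]. With the same k in both arms, the full-follow-up rate ratio divided by the truncated one is

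[1 + d1(k − 1)/2] / [1 + d0(k − 1)/2], where d1 is intervention and d0 is control.

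The documents give neither k nor a split by arm; 25% versus 15% and k = 1.5 to 3 are assumptions. The last column enters only a recoverable half (12.5% versus 7.5%).

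| k | All recoverable, 25% vs 15% | Truncated ratio 0.80 becomes | Half recoverable |
|---|---|---|---|
| 1.5 | 1.0625/1.0375 = 1.024 | 0.82 | 1.03125/1.01875 = 1.012 |
| 2 | 1.125/1.075 = 1.047 | 0.84 | 1.0625/1.0375 = 1.024 |
| 3 | 1.25/1.15 = 1.087 | 0.87 | 1.125/1.075 = 1.047 |

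- With 20% in both arms and the same k, the ratio is 1.00: no bias.
- With k = 1, there is no bias whatever the split.
- With 20% in both arms but k = 2 in one and 1.5 in the other, it is 1.10/1.05 = 1.048, so a difference in later rates alone is enough.
- If controls discontinue more, the direction reverses.

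**The case against.** The other side has a good deal to say, and most of it limits the size of the point.

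- **Not all lost follow-up is recoverable.** The 20% in Section 9.3 covers every reason for leaving. Nothing follows death, refusal may bar further review, and records may be out of reach after transplant or transfer. Requests to outside health systems may need extra permission (8.1). The documents under review do not show whether authorization survives discontinuation in every case. The figures for all discontinuers are therefore an upper bound.
- **Arm-level loss is not bias in the comparison.** With 20% discontinuing, one arm's rate is understated by 1 − 1/1.05 = 4.8% (k = 1.5) to 1 − 1/1.20 = 16.7% (k = 3). A reader might take this as the error in the treatment effect, but it cancels when the arms are alike.
- **The PI does not choose every date.** Death, transplant and a unit change are dated facts, and Section 7.3 gives criteria for loss to follow-up. Those criteria do not say which date ends follow-up: last contact, the missed visit, or the day the participant is declared lost. Discretion remains for some reasons.
- **Safeguards exist.** The DSMB reviews withdrawals (7.1), mentees are not withdrawn for not taking part (6.4), completers and non-completers are compared (9.3), and missingness is examined (9.4.2). None of these recovers an event. The DSMB review is not said to be blinded or to cover the cut-off date.
- **Sections 7.1 and 7.2 do not contradict each other.** Stopping the intervention and leaving the study are different things. The contrast shows only that record review without the intervention is already planned.
- **Records alone are not the full outcome.** Self-report ends when contact is lost, so counting full exposure from records alone could miss events at outside hospitals. This stands, and the fix has to deal with it.

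**Conclusion.** The point holds as a moderate one that is cheap to correct. Section 7.2 stops collection of primary-endpoint data that could often still be obtained, and for some reasons an unblinded PI sets the date. Neither the offset nor the ancillary completer comparison repairs truncation that is related to illness and differs by arm.

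Under the stated assumptions the rate ratio is off by about 2-9% as an upper bound, or about 1-5% if half of the discontinuations are recoverable, against a planned 20% reduction. If the arms have the same discontinuation and the same relative later rate, the bias is nil. The power cost is about four to five points in the central 12-month case, again assuming full recovery.

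A reader might infer that the intention-to-treat analysis is broken. The documents do not support that: Section 9.3 keeps discontinued participants in their assigned arm up to their last data. What is lost is completeness of follow-up. Nor do the documents show that discontinuation will in fact differ by arm; they show only a route by which it could.

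**What to change.** In Section 7.2, let discontinuation end only surveys and contact. Continue record ascertainment of ED visits and hospitalizations for every randomized participant to the T2 date that would have applied had the participant stayed, unless the participant dies or withdraws permission for record access.

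In Sections 7.2 and 9.4.2, for every discontinued participant, including those lost to contact, end follow-up time in the offset at the last date of documented record coverage, not at a PI-determined date. Record that date for each such participant.

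Add to Section 9.4.2 a sensitivity analysis that counts only record-ascertained events in both arms, because self-report stops when contact is lost.

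The cost is revised wording and a few more months of existing record abstraction for up to about 20% of participants. Some records after a transfer will remain unobtainable; for those, the coverage date shows where observation really ended.

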## 7.3 LOST TO FOLLOW-UP

A participant (either mentor or mentee) will be considered lost to follow-up if he or she fails to return for 2 or more scheduled study visits and study staff are unable to contact the participant after at least 6 attempts. We will minimize loss to follow up by inquiring with the dialysis facility about the participant's whereabouts if mentors miss 2 or more training sessions, 2 or more scheduled weekly calls to mentees and/or 2 or more telephone calls from study staff; or as mentees or usual care group if they miss 1 or more study visits, and do not return calls from study staff.

The following actions must be taken if a participant fails to return to the clinic for a required study visit:

- The site will attempt to contact the participant, reschedule the missed visit within 14 days of scheduled visit, counsel the participant on the importance of maintaining the assigned visit schedule and ascertain if the participant wishes to and/or should continue in the study
- Before a participant is deemed lost to follow-up, the investigator or designee will make every effort to regain contact with the participant (where possible, 6 telephone calls and, if necessary, a certified letter to the participant's last known mailing address). These contact attempts will be documented in the participant's study file.
- Should the participant continue to be unreachable, he or she will be considered to have withdrawn from the study with a primary reason of lost to follow-up

## 8 STUDY ASSESSMENTS AND PROCEDURES

### 8.1 ENDPOINT AND OTHER NON-SAFETY ASSESSMENTS

Refer to Section 5 for details regarding recruitment for mentors and patient participants for screening procedures to evaluate for eligibility, including execution of a HIPAA waiver prior to screening if required by local site regulations. Scoring for surveys is detailed in the PEER HD Survey Scoring guide.

#### Screening & Enrollment

**Mentors.** Potential participants will first undergo a screening of their EMR and the information will also be confirmed by interview with the patient prior to enrollment (RedCap: 'Mentor Eligibility Questionnaire From EMR'). This includes questions about the inclusion/exclusion criteria.

**Patient Participants.** Potential participants will first undergo a screening of their EMR and the information will also be confirmed by interview with the patient prior to enrollment (RedCap: 'Mentee Eligibility Questionnaire From EMR'). This includes questions about the inclusion/exclusion criteria.

#### Mentor Training Assessments

Mentors will be evaluated by *post-training* assessments. This will include the following:

- Fluid Training Survey (Module 1; 6 items)
- Uremia & Infection Training Survey (Module 2; 6 items)
- Mentor Role Training Survey (Module 3; 5 items)  
*Each of these survey items has one correct answer. Score will be reported as % correct overall.*
- Mentor Role Play Self-Assessment (Modules 3 & 4; 'Confident' Likert-type responses; 11 items)
- Formative Assessment after each module (Strongly agree to Strongly disagree; 11 items)
- Summative Assessment at the conclusion of core training (open ended questions; 5 items)

Refresher training events will only include formative and/or summative post-training assessments.

#### Baseline Visit, 3-Month (Patient participants), 9-Month (Mentor), 12 to 18-Month (T2; All)

Surveys will be completed for all visits by both mentors and patient participants, unless otherwise specified. Mentors will complete baseline surveys prior to participating in training activities.

*Baseline visit.* Include the following assessments:

- Demographics, health literacy, behaviors, and ED/Hospitalization self-reported use
- Self-report of medical history and access to care

*All visits.* Include the following assessments:

- Quality of Life (RAND SF-36)
- Depressive symptoms (CESD-10)
- Dialysis Self-management Self-efficacy (PDialSMS)

- Kidney Disease Self-Management Behaviors Index (KDBI)
- Multidimensional Scale of Perceived Social Support (MSPSS)
- Dialysis-specific Social Support Survey
- Brief Kidney-COPD Survey
- Chronic Hemodialysis Knowledge Survey (CHeKs)
- CHeKs PLUS Survey
- Communication Assessment Tool (CAT)

*Mentee group only – 3-Month Visit.* Include the following assessments:

- Health Care Climate Questionnaire (HCCQ) Long Form
- Checklist for Mentee Assessment of Mentors

*Monthly all participants.* Include the following assessment:

- Self-report of ED visits and/or hospitalizations

#### **Monthly & Quarterly Intervention Survey (Mentor)**

Study personnel will contact all mentors to monthly and perform the 'Study Staff Monthly Mentor Check-in Survey'. Additionally, mentors will perform a quarterly self-assessment.

#### **Intervention recordings & logs & phone billing record review**

Phone billing records for all mentor and mentee phones will be reviewed. All calls will be abstracted including: phone number called, date, time, and duration. A summary of weekly minutes between mentor and mentee pairs will be generated for characterization of intervention dosing as well as evaluation of execution of mentor and mentee responsibilities. If the mentor uses his/her own personal telephone to contact the mentees, the study staff may ask to review the pertinent personal telephone records with that mentor to ascertain the time spent mentoring.

Random recordings of calls will be submitted to the study team for qualitative review of content. Call logs by mentors and mentees will also be reviewed, coded and characterized for content notes.

